1.3 SCHEDULE OF ACTIVITIES

	Eligibility screening (Pre-consent)	Baseline Day 1	3-Mo Follow-up Day 90 -14/+30	6-Mo Follow-up Day 180 -14/+30
Probable OUD diagnosis (NIDA myTAPS ¹ or past 90 day receipt of MOUD)	X			
Patient health questionnaire (PHQ-9) for depression ²	X			
Probable PTSD (PC-PTSD-5) ³	X			
Age 18 or older	X			
Patient at participating clinic	X			
Current receipt of both MOUD and psychotropic medication from provider(s) outside of the participating primary care health system (exclusion criterion)	X			
Speak English or Spanish	X			
Informed consent	X			
Randomization		X		
Adverse event reporting		X	X	X
Outcome Evaluation				
MOUD continuity of care ⁴ (max number of continuous (i.e., no breaks of more than 7 days) days on MOUD; EHR review)			X	X
MOUD access (receipt of MOUD prescription within 30 days of diagnosis; EHR review) ⁵		X	X	X
MDD symptoms (PHQ-9 ² raw score change)		X	X	X
PTSD symptoms (PCL-5 raw score change)		X	X	X
Drug use frequency (NSDUH ⁶ items)		X	X	X
Opioid use severity (PROMIS Substance Use Short Form ⁷)		X	X	X
Alcohol use (AUDIT-C ⁸)*			X	X
Opioid overdose risk behaviors (Opioid Overdose Risk Assessment ⁹)		X	X	X
Opioid overdose events (Naloxone Overdose Baseline Questionnaire ¹⁰)		X	X	X
MDD remission (PHQ-9 ² score < 10)		X	X	X
MDD response (PHQ-9 ² score < 50% of baseline)		X	X	X
PTSD remission (PCL-5 score < 34)		X	X	X
PTSD response (PCL-5 score < 50% of baseline)		X	X	X
Suicidality (Columbia Suicide Severity Rating Scales ¹¹)		X	X	X
All-cause mortality (death records)			X	X
MOUD initiation ¹² (receipt of MOUD prescription within 14 days of diagnosis; EHR review)			X	X
MOUD engagement ¹² (receipt of two or more MOUD prescriptions within 34 days of diagnosis; EHR review)			X	X
Access to MDD and/or PTSD treatment (receipt of medication and/or behavioral treatment associated with diagnosis; EHR review)			X	X
Quality of care for MDD ¹³ (4 psychotherapy visits in the first 8 weeks or an adequate (12-week) medication trial)			X	X
Quality of care for PTSD ¹³ (4 psychotherapy visits in the first 8 weeks or an adequate (60-day) medication trial)			X	X

	Eligibility screening (Pre-consent)	Baseline Day 1	3-Mo Follow-up Day 90 -14/+30	6-Mo Follow-up Day 180 -14/+30
Veterans RAND 12-item General health functioning (VR-12 ¹⁴)		X	X	X
Demographics (sex, race, ethnicity, education level, marital status)		X		
Alcohol use severity (AUDIT ⁸)		X		
Pain levels (PEG Pain Monitor ¹⁵)		X	X	X

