History of MOUD treatment (items developed by research team)		X		
Current MDD/PTSD treatment (NSDUH ⁶ items)		X		
Prior experiences with Care Coordinator (items developed by research team)		X		
Interpersonal support (presence of a support person who does not have problematic opioid use)		X		
Homelessness (Homelessness Screening Clinical Reminder Tool; ¹⁶ GPRA ¹⁷ ** item)		X	X	X
Legal involvement (NSDUH items; Addiction Severity Index ¹⁸ items)		X	X	X
Disability and impairment (Sheehan Disability Scale ¹⁹)		X		
Rurality (Rural-Urban Commuting Area code ²⁰ associated with 5-digit ZIP code)		X		
Care Coordinator communication (AHRQ Consumer Assessment of Healthcare Providers and Systems ²¹)			X	
Ability to access treatment quickly (AHRQ CAHPS ²¹)			X	
Satisfaction with treatment (AHRQ CAHPS ²¹)			X	
Patient-Care Coordinator working alliance (Modified form of Working Alliance Inventory – General Practice ²²)			X	

*The full AUDIT will be administered at baseline.
 **Government Performance Results and Modernization Act of 2010.

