Our revised outcomes are as follows: (1) Buprenorphine continuity of care,⁴ which refers to the numbers of cumulative days the patient receives buprenorphine during the 180 days after study enrollment; (2) Buprenorphine access,⁵ defined as number of days until first buprenorphine prescription after study enrollment, among patients with a new episode of OUD care (i.e., no care for at least 30 days prior); (3) MDD symptom severity, as measured by the PHQ-9²; and (4) PTSD symptom severity, as measured by the PCL-5.¹⁷⁹ Buprenorphine continuity and access will be based on prescription (data and frequency) data from the follow-up assessments and New Mexico and California Prescription Drug Monitoring Program data. MDD and PTSD symptom severity will be collected in baseline and follow-up assessments, with primary outcome analyses based on final scores across the six-month period.

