3.4 Statistical models

3.4.1 Notation

Table 8 provides notation used to describe the statistical models. We note that the sample size per primary care clinic where not large enough to support the use of fixed effects by clinics in our regression models. Instead, we utilize fixed effects for health systems. When the sample sizes for the smallest health systems prove too small (e.g., less than 30 for continuous

outcomes), we will collapse the smallest health systems together for the purposes of our regression models.

Table 8: Notation used to describe the statistical models.

Notation	Description
X_{ij}	The baseline characteristics of participant i at health system j , including both demographics and other baseline characteristics.
P_{ij}	An indicator of prior MOUD treatment for participant i at health system j .
T_{ij}	The random treatment assignment of participant i at health system j .
y_{ij}	An outcome measure for participant i at health system j .
R_{ij}	An indicator denoting whether participant i at health system j responded to the 6-month follow-up survey.
M_{ij}	A mediator of the outcome-treatment relationship for participant i at health system j .

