3.4.7 Mediation analyses

We will assess several potential mediators in this study, including whether patient experiences of care and working alliance with the care coordinator at 3 months mediate the impact of CC-COD on patient. Specifically, we consider the following mediators:

1. clinician communication,
2. ability to quickly access treatment,
3. overall rating of treatment, and
4. patient Care Coordinator working alliance using a modified Working Alliance Inventory.

To ensure a proper temporal ordering of the treatment, mediators, and outcomes, all outcomes for the mediation analyses will be measured at 6-months, while the mediators will be measured at the 3-month follow-up.

All mediation analyses will follow the approach described in Imai, et al. (2010),⁶ including the technical assumptions necessary to identify causal mediation effects. This methodology requires the specification of a model predicting the mediator using only baseline information, and a model predicting the outcome using both baseline information and the mediator. For a continuous mediator and outcome, the models have the form:

$$\begin{aligned} M_{ij} &= \eta_j + \varphi T_{ij} + X_{ij} \boldsymbol{\omega} + \epsilon_{ij} \\ y_{ij} &= \alpha_j + \beta T_{ij} + \delta M_{ij} + X_{ij} \boldsymbol{\tau} + e_{ij}, \end{aligned}$$

where $\varphi * \delta$ represents the causal mediation effect under necessary technical assumptions. For binary outcomes or mediators, the models will be specified as logistic regression models. We will use the *mediation* package for the R computing environment to conduct these analyses.⁷

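### For the 6-month PHQ-9 and PCL-5 outcomes, the mediation models omit 3-month symptoms and name no sensitivity check, so patient experience can appear to mediate an effect that it does not carry

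*SAP*

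**What the plan says.** SAP 3.4.7 names four mediators: clinician communication, quick access to treatment, overall rating of treatment, and working alliance with the Care Coordinator. On timing, "all outcomes for the mediation analyses will be measured at 6-months, while the mediators will be measured at the 3-month follow-up". The mediator is modelled from arm, health system and baseline variables. The second equation is "a model predicting the outcome using both baseline information and the mediator". SAP 3.4.1 defines the covariate vector X as "The baseline characteristics of participant i at health system j , including both demographics and other baseline characteristics"; it does not name baseline PHQ-9 or PCL-5. The product φδ "represents the causal mediation effect under necessary technical assumptions". Those assumptions are not listed, and no check of them is named.

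In Protocol 1.3 the care ratings, for example the row "Satisfaction with treatment (AHRQ CAHPS", and the working alliance are marked at 3 months only. PHQ-9 and PCL-5 are marked at baseline, 3 and 6 months, and Protocol 8.1 agrees: "MDD and PTSD symptom severity will be collected in baseline and follow-up assessments". Protocol 8.1 also describes one telephone interview per follow-up wave, so ratings and symptom scores come from the same 3-month interview. The table in Protocol 3 lists 6-month PHQ-9 and PCL-5 among the mediation outcomes.

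The status of mediation is mixed. It is Hypothesis 2 and a secondary objective in Protocol 1.1, and a secondary objective in SAP 2.1.2. It is exploratory in Protocol 3, 4.1 and 8.1 and in SAP 2.5.4.

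**The concern.** The only protection that the SAP names is that mediators are measured before outcomes. That places the ratings ahead of the 6-month scores, but it does not separate them from symptoms reported in the same 3-month interview. The intervention gives weekly contacts in the first two months and monthly symptom measurement (Protocol 6.1.1), so it aims for some symptom change by 3 months. If that change colours the ratings and persists to 6 months, 3-month symptoms are a common cause of mediator and outcome. They arise after randomisation, so adjusting for baseline cannot remove their influence.

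At stake is what may be concluded about Hypothesis 2. A positive φδ could be reported as evidence that patient experience carries the effect on symptoms when it carries none.

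**Working it through.** **Stated figures.** The SAP gives no power or effect figure for mediation, so there is none to reproduce. The scale can be checked against SAP 3.5.1, using (z for two-sided 0.0125 + z for 80% power) × SD × √(4/N):
- Depression score: (2.498 + 0.842) × 6.6 × √(4/405) = 2.19; the SAP states 2.2.
- PCL-5: (2.498 + 0.842) × 17.8 × √(4/368) = 6.20; the SAP states 6.23.

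The SDs and sample sizes are therefore sound. The depression figure is 2.2/6.6 = 0.33 SD, so an assumed early effect of 0.3 SD is of the same order.

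**Set-up with no true mediation** (SD units; T = arm, S0, S3, S6 = symptoms at baseline, 3 and 6 months, M = rating):
- S3 = 0.5·S0 − 0.3·T + error (variance 0.75)
- M = c·T − k·S3 + error (variance 1 − k²), so the within-arm correlation of M with S3 is −k
- S6 = 0.6·S3 + error; M does not enter

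The values 0.5, 0.3, 0.6, k, c and n = 350 (patients with both surveys) are assumptions.

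**What the SAP models then estimate**, with S0 as the baseline covariate:
- φ = c + 0.3k
- δ = −0.6 × 0.75k / (1 − 0.25k²) = −0.45k / (1 − 0.25k²)
- total effect = −0.6 × 0.3 = −0.18
- share wrongly attributed = (c + 0.3k) × 0.45k / [0.18 × (1 − 0.25k²)]

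Example, c = 0 and k = 0.3: 0.09 × 0.135 / (0.18 × 0.9775) = 0.069.

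| c | k | Share | φδ in depression-score points (share × 0.18 × 6.6) | 95% interval excludes 0 (simulated, n = 350) |
|---|---|---|---|---|
| 0 | 0.2 | 3% | 0.04 | about 3% |
| 0 | 0.3 | 7% | 0.08 | about 9% |
| 0 | 0.4 | 12.5% | 0.15 | about 21% |
| 0 | 0.5 | 20% | 0.24 | about 31% |
| 0.25 | 0.2 | 16% | 0.19 | about 34% |
| 0.25 | 0.3 | 26% (simulated 26–27%) | 0.31 | about 66% |

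Repeat simulations move the last column by a few points at most.

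**Second parameter set** (residual SD 1, early effect 0.33 SD, path 0.6, N = 405). With c = 0 the share is k²: 4% at 0.2, 9% at 0.3, 16% at 0.4. With c = 0.25 it is 19% at 0.2 and 32% at 0.3, with intervals excluding zero in 57% and 88% of trials. With no early symptom effect at all (c = 0.25, k = 0.3), φδ is still −0.044 SD and the interval excludes zero in 66%. N = 368 gives the same pattern.

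**Adding S3 to the outcome model.** In this confounding structure the estimate returns to zero, and intervals exclude zero in 0.3–6% of trials. If the direction is reversed (T to M 0.3, M to S3 −0.3, S3 to S6 0.6), the true indirect effect is 0.3 × (−0.3) × 0.6 = −0.054 SD. The SAP models recover it, and adding S3 reduces it to about zero.

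**The case against.** A reader might infer that the no-confounding assumption fails by design. The documents do not support that. Protocol 2.2 and 3 set out the opposite direction: better experience of care raises adherence and so improves outcomes. On that theory early symptoms lie on the pathway from experience to the 6-month score, the planned model is the right one, and treating 3-month symptoms as a confounder would delete real mediation. Nothing in the documents settles the direction. What remains is that the assumption is open to doubt and unchecked, although the variable needed to probe it is collected.

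A reader might also infer that the SAP claims causality outright. It does not: the claim is conditional on assumptions, and the analysis is to follow a cited general approach to causal mediation. That caveat stands, but it names neither the assumption in doubt nor a check.

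The artefact from early improvement alone is modest: a quarter of a depression-score point or less in the table, and negligible at a correlation of −0.2. The large figures need a direct effect of treatment on ratings. Such an effect is plausible, because SAP 2.3 gives the absence of a care management team and registry as the main way in which EUC differs. It is still an assumption.

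Finally, several sections label mediation exploratory, and two of the four mediation outcomes are buprenorphine measures, to which the symptom argument does not directly apply. Both points limit the scope. They do not remove the issue, because Hypothesis 2 is also stated without that label.

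**Conclusion.** The concern holds for the 6-month PHQ-9 and PCL-5 outcomes, as a risk that the SAP leaves unchecked and not as a demonstrated failure. Under the first parameter set, 3 to 20% of the total effect is wrongly assigned to the mediator as the correlation goes from −0.2 to −0.5, and a false positive interval arises in about 3 to 31% of trials for each mediator. With a 0.25 SD direct effect on ratings these become about 16–27% and 34–66% at −0.2 and −0.3. The early effect, its persistence, the correlations, the direct effect and n = 350 are all assumed. The existence of the artefact under this structure follows from the models as written; its size in this trial is unknown. It bears on the reading of Hypothesis 2 and leaves the four primary tests untouched. A cheap improvement to the SAP is warranted.

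**What to change.** Amend SAP 3.4.7 as follows.
1. State the assumption that, given arm and baseline, nothing confounds mediator and outcome. Name baseline PHQ-9 and PCL-5 as part of X.
2. For every mediator, report the indirect effect over a range of residual correlations ρ between the two models, and the ρ at which it becomes zero.
3. For the PHQ-9 and PCL-5 outcomes, add a sensitivity analysis that models the 3-month score jointly with the mediator in both causal orders: as a treatment-affected confounder, using a method that allows for one, and as a step between experience and outcome. It should sit beside the planned model and not replace it.
4. Describe φδ as associational unless the result holds under these checks.

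The cost is SAP wording and analysis time; the 3-month scores are already in the schedule. Intervals for the indirect effects will be wider, and the two causal orders may disagree. If they do, the report should say that the data cannot tell them apart.

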3.5 Statistical power

All calculations are for 80% power at a Type I error rate of 1.25%, which accounts for the multiple primary outcomes using a Bonferroni correction to control the family-wise error rate at 5% ($0.05/4 = 0.0125$). Actual calculations use the observed loss to follow up rate in the final sample.

3.5.1 Primary outcomes

We used the observed distributions for our continuous variables including the following: for the planned power calculations were:

1. We observed a mean number of days until accessing Buprenorphine of 26.0 with a standard deviation of 31.9. Our total sample size for this analysis was 137 individuals with 6-month follow-up data.
2. Among those who initiate medication for OUD, the mean number of days of continuous treatment for OUD is 133.0 with a standard deviation is 54.1. The total sample size for this analysis was 392 individuals with 6-month follow-up data.
3. Among those with probable depression at enrollment ($\text{PHQ-8} \geq 10$), the mean depression symptoms score (PHQ-8) at 6 months of 11.5 with a standard deviation of 6.6. The total sample size for this analysis was 405 individuals with 6-month follow-up data.
4. Among those with probable PTSD at enrollment ($\text{PC-PTSD-5} \geq 3$), the mean PTSD symptoms score (PCL-5) at 6 months of 32.2 with a standard deviation of 17.8. The total sample size for this analysis was 368 individuals with 6-month follow-up data.

Under these observed outcome distributions as well as the final number of individuals with observed outcome values in our data, we have 80% power to detect:

1. A hazard ratio of at least 0.45 if we find a protective effect and see fewer days until accessing Buprenorphine. This corresponds to at least a hazard ratio of 2.25 if the direction were reversed or a 27-percentage point difference if the outcome was modeled as a binary measure. Notably, a previous study of Collaborative Care for opioid and alcohol use disorders found a 22-percentage point increase over enhanced usual care so if the effect is large in CLARO, we may be able to detect it.⁸
2. 18.3 additional days of continuous OUD treatment within the first 180 days. A growing body of evidence suggests the mortality is lower during OUD treatment, and that mortality is increased in the first four weeks after treatment cessation.⁹
3. A 2.2 point reduction in depression symptoms (PHQ-8). This provides power to detect effects below the clinically important difference for individual change of 5 points.¹⁰
4. A 6.23 point reduction in PTSD symptoms (PCL-5). A previous study of delivering PTSD treatment in primary care setting to active duty military found a reduction in PTSD symptoms of 7 points.¹¹

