For MOUD access, we changed the specification of the outcome from a binary measure to a time-to-event measure. We specify a time to event measure because ‘the number of days until first buprenorphine prescription’ is available in the Prescription Monitoring Program (PMP) and allows for more information around the distribution of times until beginning buprenorphine.

We originally proposed to use the EMR to obtain information on patient outcomes but changed the source of data to the participant surveys and PMP. We believe this increases the validity of both primary OUD endpoints the study is measuring. Previous research indicates that the EMR contains missing data at both the variable and observation levels, and that this negatively impacts the validity of quality measures.²²¹⁻²²³ In contrast, all study participants have completed the study screener that contains questions from myTAPS,¹ a clinically validated composite measure to establish probable OUD. In addition, the change in data source for prescription information will result in a more accurate measure for receipt of buprenorphine. In the EMR, providers record prescriptions that have been *written*, and the

software does not contain information on whether a patient has ever *filled* the prescription. In contrast, as required by law, the PMP includes information on both the number and duration of prescriptions for controlled substances, including buprenorphine, that have been *filled*. It also includes prescriptions that may have been written by providers outside of the health care system that the patient is assigned to as part of the study. While neither a written prescription nor a filled prescription can be considered a perfect proxy for medication that has been taken, a prescription fill provides stronger evidence for taking a medication. Where available, we include self-reported data on MOUD use from the participant follow-up surveys.

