Participant identifiers will also be entered by the Care Coordinators into the patient registry, including name, date of birth, and MRN. This data will only be accessible by pre-authorized clinic and research personnel (Research Assistants, Care Coordinators, Care Coordinator Supervisors, and Clinic Administrators) and CLARO's Behavioral Health Consultants. At study completion, the clinics will send this data to RAND SRG via Kiteworks for storage on the SRG secured segment and merged with other study data.

Identifying information will be used to obtain data on participant mortality from state vital records offices and state prescription monitoring programs (the New Mexico Prescription Monitoring Program and the Controlled Substance Utilization Review and Evaluation System). PMP data will be sent in batches with identifiers to UNM for requests made prior to 8/15/22 and RAND SRG for requests made on or after 8/15/22. The study team will link the PMP data with the CLARO study data using identifiers

and then de-identify the PMP data before providing to the the analytic team. These procedures will be reviewed by the IRB and implemented once approved.

Deidentified study data will be uploaded two times per year to the NIMH National Data Archive. A universal subject ID (Global Unique Identifier, “GUID”) will be generated for each participant and will be linked to the participants’ unique study ID assigned in REDCap. This key will be stored on CLARO secured servers and will not be accessible to anyone outside of the UNM SDCC/RAND SRG staff. All raw data will be uploaded every six months to the NIMH NDA per their policies and in accordance with UNM’s information security policies. Additionally, all analysis data sets used for manuscripts must be uploaded to the NIMH NDA, identified by GUID.

The SDCC/RAND SRG will provide deidentified analysis data sets for the final analyses. Participant-level data will be enumerated with their study IDs and no MRNs or other personal identifying information will be shared with them. Data will be transmitted via RAND’s secured data transfer protocol, Kiteworks.

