2.7 Randomization

After a baseline assessment, study participants will be randomized 1:1 into CC-COD/CC-COD+ or EUC. A stratified randomization design will be used, with the strata determined by primary care clinic and prior MOUD exposure. A randomization list will be generated for each stratum and include randomly permuted block sizes of 2 and 4. We will stratify on prior MOUD to mitigate confounding, as patients who have used MOUD previously are more likely to initiate MOUD subsequently. Research staff will access the randomization module in REDCap. Staff will enter which prior MOUD exposure stratum and clinic the patient is in, and the intervention arm assignment will be generated.

We extended the randomized trial from the original study to implement CC-COD+. All participating clinics started the study with enrolled patients being randomized between CC-COD and EUC. Three health systems then transitioned to randomizing patients between CC-COD+ and EUC. The remaining health system did not transition to CC-COD+ because they did not enroll sufficient patients to justify transitioning to CC-COD+. Table 5 provides a timeline of when health systems transitioned to CC-COD+.

Table 5: Competitive Revision Recruitment Timeline

Site Groups	Date of CC-COD+ Transition
Health System 1 (includes 7 clinics)	08/29/2022
Health System 3 (includes 3 clinics)	07/13/2023
Health System 4 (includes 3 clinics)	08/28/2023

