3.4.2 Overview and General Principles

The primary analyses will be performed for the intention-to-treat population, which consists of all randomized subjects. All individual statistical hypotheses will be tested using two-sided tests, with adjustment for multiple testing using a Bonferroni or Benjamini-Hochberg correction. Primary outcomes will be analyzed at a Type I error rate of 1.25% to control the family-wise error rate at 5% (e.g., so $0.05/4=0.0125$ when using a Bonferroni correction or the first p-value threshold for significance with Benjamini-Hochberg). Similarly, secondary and exploratory outcomes will be analyzed at Type I error rates to control family-wise error rate at 5% within domain. See Table 2 and 3 for definition of secondary outcome domains and our exploratory outcomes.

Outcomes derived from the follow-up surveys are subject to nonresponse, and statistical hypotheses based on these outcomes will be tested using nonresponse weighted models, if necessary. Traditionally, a logistic regression model can be specified predicting response using the demographic characteristics listed in Table , the baseline characteristics listed in Table , and the randomized treatment assignment. The model is given by:

$$\log \left(\frac{\Pr(R_{ij}=1)}{1-\Pr(R_{ij}=1)} \right) = \eta_j + \mathbf{X}_{ij} \boldsymbol{\theta} + \gamma T_{ij} + \rho P_{ij}$$

where η_j represent health system fixed effects. The nonresponse weight for participant i in health system j is given by $w_{ij} = \frac{1}{p_{ij}}$, where $p_{ij} = \Pr(R_{ij} = 1)$. However, we will utilize a nonparametric machine learner to estimate our nonresponse weights to allow for more complex relationships between the predictors variables and the odds of being a responder, thereby producing more high-quality nonresponse weights if they are deemed necessary.

To assess whether there is a need for use of nonresponse weights in our final analyses, we will assess how representative our sample of responders is for each outcome using effect sizes (ES) differences. If most of the ES differences are small (e.g., less than 0.1 or 0.2), we will feel good about the representativeness of our sample of responders to the original baseline sample and not utilize nonresponse weights in our final analyses.

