3.4.5 Survival outcome

Buprenorphine access, the survival outcome that is measured in the PMP and survey will be analyzed using a Cox proportional hazard regression model including health-system, prior MOUD exposure, and treatment assignment as predictors. The Cox proportional regression model is given by:

$$h(t) = h_0(t) * \exp(\alpha_j + \nu P_{ij} + \beta T_{ij})$$

where α_j are health system-level fixed effects, and e^β is the hazard ratio effect of CC-COD over EUC. The statistical hypotheses from the Cox proportional hazard regression will be of the form:

$$H_0: \beta = 0 \text{ vs}$$
$$H_1: \beta \neq 0.$$

Outcomes that are measured as part of the 6-month follow-up survey may be weighted to account for nonresponse as previously described. Again, if we do not have sufficient sample size to support modeling P_{ij} (prior MOUD treatment), then it will be removed from a given model. We will assess this for each continuous outcome by examining if we have at least 30 individuals with and without prior MOUD treatment in our analytic sample. We will right censor all observations for those individuals who did not ever receive buprenorphine during the course of follow-up for these analyses.

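### As written, the plan lets the buprenorphine access analysis depend on survey response, although the endpoint can be observed in prescription monitoring data without an interview

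*SAP*

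**What the plan says.** **Population.** SAP 3.4.2 states: "The primary analyses will be performed for the intention-to-treat population, which consists of all randomized subjects". The footnote to SAP Table 1 defines study participants as everyone who consented and was randomized. Protocol 9.3 limits access to randomized participants with a new OUD episode and mentions no survey condition.

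**Source.** SAP Table 1 lists survey and PMP for access. Protocol 8.1 explains the move to the PMP: it records filled prescriptions, including those written outside the patient's health system. It then adds: "Where available, we include self-reported data on MOUD use from the participant follow-up surveys". Linkage uses identifiers. Protocol 10.1.3 says: "Identifying information will be used to obtain data on participant mortality from state vital records offices and state prescription monitoring programs".

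**Sizing.** SAP 3.5.1 says of access: "Our total sample size for this analysis was 137 individuals with 6-month follow-up data". The same description of follow-up is attached to the PHQ and PCL-5 samples, which come from the survey alone. SAP 3.5 says that the calculations use the observed loss to follow-up.

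**Weights.** SAP 3.4.5 covers one outcome, access, and says: "Outcomes that are measured as part of the 6-month follow-up survey may be weighted to account for nonresponse as previously described". SAP Table 8 defines the response indicator behind those weights as response to the 6-month survey. Protocol 9.4.2 names nonresponse weighting only for the two symptom scores, and Protocol 9.2 names the expected loss to follow-up only for them.

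**Censoring.** SAP 3.4.5 right-censors people who never receive buprenorphine during follow-up. It gives no censoring date.

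**The concern.** Someone who misses the month-6 call may still have PMP data for the whole 180 days. Two things can then go wrong.

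First, if the Cox model is fitted to survey responders, weighted or not, randomized people whose outcome is observable are left out and the comparison is no longer the intention-to-treat one that the SAP declares.

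Second, even with everyone included, a responder's event can be found through the PMP or through self-report, whereas a month-6 non-responder's must come from the PMP or an earlier interview. If response differs by arm, the hazard ratio picks up a difference in detection. Response could differ: participants know their assignment (Protocol 6.3), and intervention patients have at least 13 planned coordinator visits (Protocol 6.1.1). The documents give no response rates by arm, so neither the direction nor the size of any bias is known.

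**Working it through.** **1. Can the text be read as a responder analysis?** Three features of the SAP point that way: the follow-up description attached to the 137, the use of observed loss to follow-up, and a weighting sentence in a section that has only one outcome. The weights are the inverse probability of responding to the 6-month survey, so they have meaning only for responders. If weights are judged unnecessary, SAP 3.4.2 describes relying on how well the responders represent the baseline sample. Against this stand SAP 3.4.2, the Table 1 footnote and Protocol 9.3. No sentence settles the matter.

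**2. Reproduce the SAP's figure.** Inputs:
- Error rate and power, SAP 3.5: "All calculations are for 80% power at a Type I error rate of 1.25" percent.
- Sidedness, SAP 3.4.2: "All individual statistical hypotheses will be tested using two-sided tests".
- Allocation, SAP 2.7: "study participants will be randomized 1:1 into CC-COD/CC-COD+ or EUC".
- Detectable hazard ratio, SAP 3.5.1: 0.45, or 2.25 reversed.

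The event count is not given, so I solve for it with Schoenfeld's formula:

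events = 4 × (2.498 + 0.842)² / (ln HR)² = 44.60 / (ln HR)²

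- HR 2.25: 44.60 / 0.6576 = 67.8 events
- HR 0.45: 44.60 / 0.6376 = 70.0 events

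The stated effect thus implies about 68 to 70 events, roughly half of 137 (67.8/137 = 49.5%). Had all 137 had events, the detectable HR would be exp(2 × 3.339/√137) = 1.77. The figure is coherent with 137 people, but that does not show who they are.

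**3. What inclusion could change (illustration only).** Assume that the 137 are survey responders and that the overall response rate applies to new-episode participants. SAP 2.6 gives 797 randomized; SAP Table 9 gives 525 for most of the all-participant survey outcomes.

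- Response: 525/797 = 65.9%
- Eligible: 137 × 797/525 = 208, so 71 more people

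The detectable HR is exp(2 × 3.339/√events). It depends on how often the 71 have an event:

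| Event fraction in the 71 | Total events | Detectable HR |
|---|---|---|
| Same as the 137 (49.5%) | 103.0 | 1.93 |
| Half of that | 85.4 | 2.06 |
| None | 67.8 | 2.25 |

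With the same event fraction throughout, other assumed response rates give:

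| Response rate | Eligible | Events | Detectable HR |
|---|---|---|---|
| 80% | 171 | 84.8 | 2.07 |
| 70% | 196 | 96.9 | 1.97 |
| 60% | 228 | 113.0 | 1.87 |

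If the 137 already includes every randomized new-episode participant, none of this applies and the figure stays at 2.25.

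**4. Ascertainment.** No arithmetic is possible, because no counts are given for PMP-only events, survey-only events or response by arm. What can be shown is the absence of a rule: none covers participants with PMP data only, disagreement between the sources, or the date of censoring.

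**The case against.** A reader might infer that survey drop-outs are excluded, that intention-to-treat is broken and that about 71 people are discarded. The documents do not support that. The 137 stands in a power section, no analysis section removes non-responders, and people without buprenorphine are censored, not dropped. The follow-up wording is undefined and could include PMP follow-up. SAP 3.5.1 also describes its counts as people with observed outcome values, and Protocol 7.3 gives lost-to-follow-up status only when follow-up health record data are unavailable as well. The weighting sentence is permissive and resembles sentences in SAP 3.4.3 and 3.4.4. All of this stands, and it limits the point to what the plan permits.

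A second tempting reading is that access must be derived from the PMP alone. Protocol 8.1 combines the sources deliberately, and the PMP data cover only New Mexico and California. Which derivation is primary is partly a judgement.

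Third, if people who miss interviews also tend to leave treatment, they would have fewer events and the gain in power would shrink. The documents give no figure for this, so the range above runs to zero added events.

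The objection does not remove the dependence of event detection on survey response, which follows from the data-source rule itself. Nor does it explain why a section with access as its only outcome allows survey weights when Protocol 9.4.2 confines them to symptom scores.

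**Conclusion.** The concern holds in a limited form. For a primary endpoint that can be observed without an interview, the plan permits restriction to survey responders and makes event detection depend on survey response. Both are in tension with the stated population. It is not shown that anyone is in fact excluded: the number randomized with a new episode and the number of events are both missing.

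The effect on power is conditional. At the overall response rate the detectable HR lies between about 1.93 and 2.25, depending on events among non-responders, and it is unchanged if the 137 is complete. This rests on Schoenfeld's approximation and on the assumption that the overall response rate carries over to new-episode participants. The size and direction of any ascertainment bias are unknown. The point goes beyond missing detail, because an analyst could follow the plan and arrive at the weaker analysis.

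**What to change.** 1. In SAP Table 1 and 3.4.5, state that access includes every randomized new-episode participant with PMP linkage, whatever their survey response, censored at day 180 (or at death or withdrawal) if no buprenorphine is recorded.
2. State that survey nonresponse weights do not apply to this endpoint.
3. Apply the same inclusion rule to buprenorphine continuity, within that endpoint's own stated population.
4. Pre-specify a PMP-only analysis in the same set, at least as a sensitivity analysis, to check for differential ascertainment.
5. Say whether the 137 leaves out non-responders who have PMP data. Restate the access sample size, the event count and the detectable hazard ratio on the full set.

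The cost is SAP wording, a re-derivation from PMP data that the protocol already plans to obtain, and analyst time. No new data collection is needed. In the PMP-only analysis, self-reported use that is absent from the PMP would not count, which is a reason to report it beside the combined measure.
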